7.1 Specification of Safety Parameters

Minor risks associated with acupuncture are anticipated to occur in less than 5% of participants. Over the course of the study, which will include 48 patients and a maximum of 576 acupuncture treatments, we might expect 5% of patients to have minor side effects and do not expect any serious adverse events. Any adverse event rate over 5% in 12 months will be reported to the UCSF IRB and NIH/NCCIH.

7.2 Methods and Timing for Assessing, Recording, and Analyzing Safety Parameters

The safe profile and low risks of acupuncture have been well documented in the literature.⁴³⁻⁴⁵ A summary of key findings by severity of adverse events is listed below:

- Serious adverse events are very rare. Two prospective surveys conducted in the United Kingdom, which included over 65,000 acupuncture treatments reported no serious adverse events.^{43,44} A prospective study in Germany of 229,230 patients who received a total of 2.2 million acupuncture treatments, reported two cases of pneumothorax.⁴⁵
- Minor adverse event rates occur in less than 15 per 10,000 treatments.^{43,44} The most common minor adverse events were bleeding or hematoma (estimates range from 2.1% to 6.1%), needling pain (< 2%), and aggravation

of symptoms (< 3%).

- Mild transient reactions include feeling relaxed (11.9%) or energized (6.6%), tiredness (2.6%), drowsiness (1.1%), dizziness (0.6%), nausea (0.3%), feeling faint (0.2%).

7.3 Adverse Events and Serious Adverse Events

An **adverse event (AE)** is defined as any unfavorable and unintended diagnosis, symptom, sign (including an abnormal laboratory finding), syndrome or disease which either occurs during the study, having been absent at baseline, or if present at baseline, appears to worsen. Adverse events will be recorded regardless of their relationship to the study intervention.

A **serious adverse event (SAE)** is defined as any untoward medical occurrence that results in one or more of the following outcomes:

- Death
- A life-threatening event
- Inpatient hospitalization or prolongation of existing hospitalization
- A persistent or significant disability/incapacity
- A congenital anomaly or birth defect
- An important medical event based upon appropriate medical judgment

Information on minor adverse events will be collected as solicited events. These will be listed in alphabetical order on an electronic case report form. Study staff will collect this information at participants' weekly visits. Using an electronic data collection system, such as RedCap or Qualtrics, helps to assure that the reporting and data collection systems avoid double capture. Describe which AEs will be collected as solicited events. The adverse event form will also have items to capture any unsolicited events such as serious adverse events; these will be documented by study staff without direct input from participants. Adverse events will be reported on a monthly basis to the data and safety independent monitor. Serious adverse events will be reported immediately.

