4.4 Data Collection and Randomization

- Following the consent process, CRCs will conduct a baseline assessment with study participants. Baseline data collection will include sociodemographic, pain symptoms, mood, daily activities and open-ended questions regarding social isolation, stigma, and experiences with pain care.
- After the baseline assessment, participants will be randomized to one of four groups (described in more detail below). To maintain participant flow and adequate staggering of acupuncture and IGMV, we will use computer-generated, randomly permuted blocks of 4 and 8, stratified by language. The database manager who will not be involved with enrollment will program the random allocation sequence; no other study staff will have access to generating the randomization sequence. The CRC will access the allocation

sequence using a programmed database that cannot be altered once the randomized condition is revealed.

- Participants randomized to study interventions will participate in weekly sessions for twelve weeks and those randomized to Integrative Group Medical Visits have the option to participate in focus groups immediately following the final weekly session.
- Three months after baseline, participants will complete validated surveys about pain symptoms, social isolation, quality of life, and other pain-related symptoms and open-ended questions about pain management.
- Three months after baseline, participants will also complete semi-structured interviews on participants' experiences living with chronic pain, and their perspectives on non-pharmacologic pain treatment, including participation in the study.
- Interviews will focus on participants' experiences treating chronic pain, perspectives on non-pharmacologic treatment, and experiences referring patients to the Integrative Pain Management Program (i.e., the larger RCT component of this study). These interviews will last 45-60 minutes and take place in-person or virtually at a private location of the participant's preference (e.g., the participant's office, UCSF Osher Center for Integrative Health offices, or via Zoom). At the time of the interview, participants will complete a brief demographic form (including gender, racial and ethnic identity, years of clinical experience, and chronic pain treatment experience). No EHR data of any kind will be collected for providers participating in the provider interview subsample.

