5. STUDY INTERVENTIONS

Study interventions are based on stakeholder input and patient preference, and the extent that they: (1) reflect real world practices that are viable options in primary care safety net settings, and (2) could be standardized to enhance replicability in future studies or in clinical practice. Study participants will be randomized to one of four experimental conditions:

- i. Usual care. Participants will receive care as usual provided through their primary care providers. Usual care includes medical diagnostic evaluation, analgesic drug therapies, recommendations for physical activity, and sometimes referral to specialist physicians or physical therapy. Usual care was chosen as a comparison arm for this study because it is practical and clinically relevant. One challenge with using a usual care arm in a clinical trial is the potential variability in the care provided in clinical practices.²⁰ EHR data will be extracted and reviewed to accurately describe usual care for study participants.

ii. **Integrative Group Medical Visits for Pain.** IGMV will consist of a 12-week program that provides education on the biopsychosocial model of pain and multimodal treatments; physical movement; mindfulness training; and peer support. Non-pharmacologic approaches were chosen based on guidelines on chronic pain management; feedback of experts, staff, and patients,²¹ and feasibility with the greatest potential to benefit participants. Participants will receive a binder with educational materials. Weekly IGMV sessions will be two hours in a group meeting space at the clinics. Sessions will start with a “check-in” where participants can share their emotions, thoughts, hopes, and fears related to their health and provide updates since the last session. Group sessions will be led by a primary care provider and a health educator and will include psychosocial support, tools for pain self-management, and psychoeducation for pain management.^{22,23} Following the group “check-in,” an invited guest (example: pharmacist, mindfulness expert) will provide information on

educational topics, including neurobiology of pain, medication safety, and connections between mood and pain (see table 1 for sample content based on prior IGMV), as well as participatory activities such as therapeutic movement or mindfulness practice.

Table 1. Sample IGMV Content

Week	Content	Facilitator(s)*

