7. SAFETY ASSESSMENTS

Participant safety will be continually monitored once an individual is enrolled in the study. Study staff will complete adverse event reporting on a weekly basis for all participants. Potential adverse experiences with group acupuncture include: agitation, anxiety, bleeding, bruising, contact dermatitis, dizziness/lightheadedness, fatigue, increased pain, redness/infection, soreness of muscles, swelling of arm/leg/other, tearfulness, weakness. Most risks associated with acupuncture are considered minimal side effects that resolve on their own.

Depending on the severity of an adverse event, modifications will be made to study participation. If an adverse event occurs that affects a participant's ability to come in for study treatments or assessments, study staff will gauge the participant's willingness to continue data collection in alternative ways such as over the phone or in-person at their home. If at any point in the study, participants report severe depressive symptoms or severe pain, research assistants will be instructed to refer participants to their primary care provider. In a situation that requires immediate attention, research assistants will notify a healthcare professional to follow-up with participants as needed. The medical team will follow standard protocol to ask appropriate follow up questions to assess the need for psychiatric evaluation for the participant.

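### Adverse events are defined against baseline, but no baseline use of the solicited symptom form is described, its content is unspecified, and section 7 names no IGMV risk

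*Combined protocol and SAP*

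**What the plan says.** Section 7.3 of the combined protocol and SAP defines an adverse event as an unfavorable sign, symptom or diagnosis "which either occurs during the study, having been absent at baseline, or if present at baseline, appears to worsen". Events are recorded whether or not they are related to the intervention.

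On collection, section 7.3 states: "Information on minor adverse events will be collected as solicited events". They are to be listed alphabetically on an electronic form, and "Study staff will collect this information at participants' weekly visits". The list itself is not given. Where it should stand, the text reads: "Describe which AEs will be collected as solicited events". The form also has items for unsolicited events, which staff complete without asking the participant directly.

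The only symptom list is in the introduction to section 7: "Potential adverse experiences with group acupuncture include: agitation, anxiety, bleeding, bruising, contact dermatitis, dizziness/lightheadedness, fatigue, increased pain", followed by redness or infection, muscle soreness, limb swelling, tearfulness and weakness. The same section says: "Study staff will complete adverse event reporting on a weekly basis for all participants".

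Section 4.4 places the baseline assessment before randomization: "Baseline data collection will include sociodemographic, pain symptoms, mood, daily activities and open-ended questions". Section 6.2 adds PROMIS and other scales, and takes concomitant conditions from the medical record.

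Section 5 describes IGMV as education plus "physical movement; mindfulness training; and peer support". The sample content table there includes sessions with a yoga instructor and a session on self-massage.

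**The concern.** The definition needs each symptom's status before treatment. A form first used after assignment does not supply it, and chronic pain patients may well have some of the listed symptoms already. Whether a weekly report is new, worse or unchanged then depends on memory. Section 3 states that participants, practitioners and assessors are not blinded, so that memory is exercised with the assignment known.

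The second part is coverage. Section 7 lists and quantifies acupuncture effects only, and section 7.5 describes event follow-up at acupuncture visits. IGMV involves movement and personal sharing in a group, which carry different possible harms. At stake are the reliability of event classification, the meaning of the 5% reporting trigger in section 7.1, and whether harms are sought equally for the two interventions.

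**Working it through.** **Step 1. The plan's own figure.** Section 7.1 gives 48 patients and at most 576 acupuncture treatments: 48 × 12 = 576, which reproduces. It does not match section 9.1, which enrolls 40 with 20 assigned to each intervention: 20 × 12 = 240, and even 40 × 12 = 480. This is a separate inconsistency to reconcile, but it means the trigger has no settled denominator.

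**Step 2. Listed symptoms against the described baseline.** The section 7 list has 13 items.

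| Items | Baseline status available? |
|---|---|
| Increased pain (1) | Yes: pain is measured, and the item itself asks about change |
| Anxiety (1) | Yes: PROMIS anxiety scale and baseline mood |
| Agitation, tearfulness (2) | In part: mood is assessed, but neither item is named |
| Bleeding, bruising, contact dermatitis, redness/infection (4) | Not named, but mostly acute and visible |
| Dizziness, fatigue, muscle soreness, swelling, weakness (5) | No item-level status described |

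The count is 1 + 1 + 2 + 4 + 5 = 13. The gap is clearest for the last five. The sleep and general well-being scales in section 6.2 may touch on fatigue, but the document does not give their items. The medical record lists conditions and is not described as recording these symptoms and their severity at enrollment.

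**Step 3. How many errors matter.** Section 7.1 requires reporting of any adverse event rate above 5% in 12 months, without a unit or denominator. Assume it is counted per participant:

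- 20 acupuncture participants: 5% × 20 = 1, so 2 exceed it (2/20 = 10%).
- All 40: 5% × 40 = 2, so 3 exceed it (3/40 = 7.5%).

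Counted per treatment, 5% × 240 = 12, so 13 would be needed and this small-number argument would not apply in the same form.

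**Step 4. Worst-case illustration.** Let q be the share of participants with at least one listed symptom before treatment. q is not in the documents. Suppose every such symptom were wrongly recorded as an event. With pre-existing symptoms alone, the chance of exceeding the trigger is P(X ≥ 2), X ~ Bin(20, q), or P(X ≥ 3), X ~ Bin(40, q). Adding a true new-event proportion of 5%, the apparent proportion is 1 − 0.95(1 − q).

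| q | Pre-existing only: of 20 / of 40 | Apparent proportion with 5% true events | Both: of 20 / of 40 |
|---|---|---|---|
| 0 | – | 5% | 0.26 / 0.32 |
| 10% | 0.61 / 0.78 | 14.5% | 0.81 / 0.94 |
| 20% | 0.93 / 0.99 | 24.0% | 0.97 / 0.998 |
| 30% | 0.99 / above 0.99 | 33.5% | 0.997 / above 0.999 |

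The first row is perfect classification: the trigger is exceeded about one time in four or three even then. The other rows are upper bounds, because they suppose that the definition fails every time.

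**Step 5. IGMV coverage.** Section 3 plans four arms of 10, so 10 + 10 = 20 of 40 participants are assigned to IGMV, and 10 of those have no acupuncture visits. Falls, strains during movement and breaches of confidentiality in a group appear nowhere in section 7. If the form follows the section 7 list, those harms are left to the unsolicited items.

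**The case against.** A reader might infer that pre-existing symptoms are counted as events. The definition says otherwise: an unchanged symptom is excluded, the form records relatedness and severity, and the team reviews events weekly (section 7.4). The missing baseline makes that judgement less reliable; it does not reverse it.

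A reader might also infer that the form asks about acupuncture effects only, and that IGMV harms go unasked. The documents do not establish this. The form's content is not stated, and the section 7 list is the likely source only because both are alphabetical. Agitation, anxiety, tearfulness, increased pain and muscle soreness could equally arise from movement or group sharing. Reporting covers all participants, and section 7.4 extends treatment of acute reactions to any procedure. The consent form, which describes risks, is not in the reviewed text.

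It would also go too far to call the resulting event rate meaningless. Arms can be compared, since background symptoms should be similar across randomized groups. That helps with a between-arm contrast, but less with a single rate set against 5%. The comparison also assumes that events are collected alike in all arms; section 4.4 describes weekly sessions only for participants assigned to an intervention. The trigger leads to a report to the IRB and NIH/NCCIH, and no stopping rule is attached to it. The pilot's stated aims concern feasibility and outcome data, not harm rates.

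These points narrow the concern. They do not supply item-level baseline status for the five symptoms, a specified list, or a stated solicited route for harms such as falls or breaches of confidentiality.

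**Conclusion.** The concern holds in a limited form. Followed as written, the plan classifies some solicited symptoms against a baseline that it does not describe collecting, with participants and assessors unblinded. The gap is about five of the 13 listed items, if that list is the form. Harm capture is oriented to acupuncture in what the document specifies, although half the participants are assigned to IGMV.

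The firm part of the size is the count: 2 of 20 or 3 of 40 exceed 5%, on a per-participant reading that section 7.1 does not confirm. The probabilities are a worst-case illustration, resting on an assumed prevalence and total misclassification. Part of the trigger's fragility comes from small numbers and its undefined unit, which a baseline form would not cure. This should be changed before enrollment, but it does not undermine the feasibility outcomes.

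**What to change.** - In sections 4.4 and 7.3, have every participant complete the solicited form once at the baseline assessment, before randomization, with severity per item. Classify each weekly report against that record as new, worse or unchanged.
- In section 7.3, replace the template instruction with the actual list.
- Add a few IGMV-relevant items not already covered, asked in all arms: for example fall, strain during movement, distress after group sharing, breach of confidentiality. State how the weekly form reaches the waitlist arm, since section 7 already commits to weekly reporting for everyone.
- While editing section 7.1, state the unit and denominator of the 5% trigger and reconcile 48 patients and 576 treatments with section 9.1.

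The cost is one extra use of an existing form and a few added items: a few minutes of participant time, with no added visits or staff.

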- The full enrollment period for the study will take place in waves over 2-3 months depending on the rate of recruitment and the success of enrollment. Once the initial 6 participants are enrolled and consented, they will be randomized to the three treatment arms (randomization procedures are included in Section 4.3). Data collection and treatment will begin for the initial 6 participants while recruitment and enrollment continue on a rolling basis for the remaining study participants. The estimated duration of study involvement for each participant is approximately six months, which includes a 12-week intervention and a 3-month follow up interview post-intervention.
- Description of intervention and administration: All study participants will receive usual care. In addition, some participants will be randomized to receive group acupuncture for a period of 12 weeks, once per week. Some participants will be randomized to receive integrative group medical visits for a period of 12 weeks, once per week.

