7.5 Follow-up for Adverse Events

Any adverse event reported by participants will be followed until resolved or considered stable. At subsequent acupuncture treatment visits, study staff will ask participants about the status of the reported adverse event at least once or until the participant reports that the adverse event has resolved.

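### Weekly adverse-event reporting is promised for all participants, but the stated solicitation route misses usual care and the stated status check misses usual care and IGMV-only

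*Combined protocol and SAP*

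**What the plan says.** Section 7 (Safety Assessments) sets the commitment: "Study staff will complete adverse event reporting on a weekly basis for all participants". It names no mode of contact.

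Section 7.3 gives the mechanism for minor events, which are solicited from a checklist: "Study staff will collect this information at" the participants' weekly visits. It also says that AEs are recorded whatever their relationship to the intervention.

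Section 7.5 opens with a rule for everyone: "Any adverse event reported by participants will be followed until resolved or considered stable". The procedure that follows is narrower: "At subsequent acupuncture treatment visits, study staff will ask participants about the status of the reported adverse event".

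Who has weekly visits follows from Section 3. For acupuncture: "some participants will be randomized to receive group acupuncture for a period of 12 weeks, once per week". For IGMV: "Some participants will be randomized to receive integrative group medical visits for a period of 12 weeks, once per week". For usual care, Section 5 says only: "Participants will receive care as usual provided through their primary care providers". No weekly study visit is described for that arm. After baseline, the contacts that Section 4.4 names for all participants are the survey and the interview at three months.

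**The concern.** Section 7 makes a promise that the procedures in 7.3 and 7.5 cannot keep for every arm. Staff working from 7.3 would ask the acupuncture, IGMV and combined arms about minor events each week, and would have no occasion to ask usual care. Staff working from 7.5 would check the status of a reported event only where there is an acupuncture visit.

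This matters because several events that Section 7 lists for acupuncture, such as increased pain, fatigue, anxiety and weakness, can plausibly occur in people with chronic pain who receive no study intervention. Usual care is the arm that would show this background. If it is not asked, even a simple listing by arm would tend to show an excess in the active arms. The pilot is also meant to test assessment procedures for the larger trial, which Section 9.1 puts at 360 participants, so a gap left here could carry forward.

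**Working it through.** The plan gives no figure to reproduce. The check is a count of stated contacts, followed by an illustration.

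**Step 1. Contacts by arm.** Inputs: four arms of 10 (Section 3), weekly sessions for 12 weeks (Sections 3 and 5), solicitation at weekly visits (7.3), status checks at acupuncture visits (7.5).

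| Arm | n | Weeks with a visit at which minor events are solicited | Acupuncture visits for status checks |
|---|---|---|---|
| Usual care | 10 | 0 | 0 |
| IGMV only | 10 | up to 12 | 0 |
| Acupuncture only | 10 | up to 12 | up to 12 |
| Both | 10 | up to 12 (up to 24 sessions) | up to 12 |

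No stated solicitation route: 10 of 40. No stated status-check route: 10 + 10 = 20 of 40.

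**Step 2. Size of the ascertainment effect.** Assume, for illustration only, that each participant in every arm has the same weekly probability w of a minor event, that weeks are independent, and that each contact captures that week's events. The chance of at least one recorded event over k solicited weeks is 1 − (1 − w)^k. The values of w are assumptions; the protocol gives none. The row k = 6 uses the adherence goal in Section 6.1 (a mean of six sessions).

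| Solicited weeks | w = 0.5% | w = 1% | w = 2% | w = 5% |
|---|---|---|---|---|
| k = 12 | 5.8% | 11.4% | 21.5% | 46.0% |
| k = 6 | 3.0% | 5.9% | 11.4% | 26.5% |
| k = 0 (usual care, as written) | 0% | 0% | 0% | 0% |

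For example, 1 − 0.99^12 = 0.114. With equal true rates, the recorded difference between a fully attending active arm and usual care would be 11.4 points at w = 1%, all of it from ascertainment. With 10 per arm, one affected participant moves an arm's rate by 1/10 = 10 points.

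**Step 3. The 5% threshold.** Section 7.1 requires reporting when the AE rate is over 5% in 12 months, without stating the denominator. Take two affected participants, both in solicited arms:

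- All randomized: 2/40 = 5.0%, not over the threshold.
- Solicited arms only: 2/30 = 6.7%, over it.
- Acupuncture recipients only: 2/20 = 10.0%, over it, and usual care plays no part.

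Section 7.1 does not settle the choice. It counts 48 patients and 576 treatments (48 × 12), whereas Sections 3 and 9.1 give 40 participants with 20 per intervention.

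**The case against.** The strongest reply is that Section 7 already requires weekly reporting for all participants, so usual care is covered and only the mode of contact is unstated. That is right as to intent. But 7.3 is the only place that says how minor events are solicited, and it uses visits that usual care does not have. The 24-hour number in Section 7.6 relies on the participant to call about lasting problems or emergencies. The phone calls in Section 8 are named for checking discontinuation criteria. Neither is solicitation of minor events, though both mean that capture in usual care need not be nil.

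Other limits stand in full:

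- A reader might infer that IGMV-only participants are also missed for new events. They are not: they attend weekly and lack only the acupuncture visits used for status checks.
- A reader might infer that the follow-up rule biases event rates. It concerns events already reported, so it affects data on resolution and not incidence.
- A reader might conclude that a planned safety comparison is invalid. Section 9.2 lists between-group analyses of patient-reported outcomes and none of AEs. With 10 per arm, such a comparison would say little even with perfect ascertainment.
- A reader might conclude that the 5% threshold is biased. The sentences before it concern acupuncture risks. If it covers acupuncture recipients only, both relevant arms have weekly solicitation and status checks, and the point falls away.
- The combined arm need not be asked 24 times. Collection is described as weekly, so 12 is the natural reading.

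**Conclusion.** The concern holds in a limited form. Sections 7, 7.3 and 7.5 do not agree, and following the visit-based procedures would under-ascertain new minor events in the 10 usual-care participants relative to the three active arms. For the 20 usual-care and IGMV-only participants, reported events have no stated status check, despite the general rule in 7.5 that every event is followed. Any descriptive AE table by arm would need to be read with this in mind.

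The size in event terms cannot be fixed from the documents. The range from 3.0% to 46.0% of participants with a recorded event, against 0% in usual care, rests on assumed weekly probabilities and on there being no capture outside visits; the 24-hour number or informal contact would narrow the gap. The effect on the 5% threshold depends on the denominator. The documents do not support saying that AE rates are non-comparable across all arms or that a planned analysis is invalid. This should be corrected before the procedures are used or carried into the main trial, and the correction is small.

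**What to change.** 1. Reconcile Sections 7, 7.3 and 7.5. State how the weekly commitment is met for participants without weekly visits, using the same solicited form at the same interval in all four arms.
2. Tie the status check on a reported event to the next study contact of any kind, so that it applies in usual care and IGMV-only as well.
3. Add the same checklist for all 40 participants at the existing 3-month survey, as a supplement to weekly capture and not a replacement for it.
4. In any table by arm, show visit-solicited events separately from those obtained by other routes.
5. State the denominator of the 5% threshold in Section 7.1.

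The cost is a few sentences of protocol text, a brief weekly contact for the 10 usual-care participants, and one added form at an existing assessment. The 3-month checklist has limits. Participants are not blinded, and recall may differ between those prompted weekly and those not. It will also miss those who do not complete the survey: at the 80% retention goal in Section 6.1, that is 0.20 × 40 = 8 participants. It therefore cannot by itself serve as an unbiased between-arm measure.
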